## 12.3 Recording and Reporting Procedures for non-CTIMP SUSARSI

It is extremely unlikely that any research related SUSARs will occur given the intervention (addition of CAD device) does not alter standard care. If however, in an unforeseen way a

non-CTIMP SUSAR does occurs during the study, it should to be reported to the Sponsor, within 24 hours, as per Portsmouth Hospitals University NHS Trust's standard operating procedure PHT/RDSOP/007 (see details above) and the Chief Investigator. The REC that approved the study will also need to be notified within 15 days of the Chief Investigator becoming aware of the event as per Health Research Authority safety reporting guidelines.

# **13. DATA HANDLING AND RECORD KEEPING**

## 13.1 Data Collection

Patients will be allocated a unique anonymised study ID number, in which their data will be collected against, to maintain participant confidentiality. A paper Case Report Form (CRF) will be created for data collection for those participating in the trial. This will be contemporaneously populated by a delegated member of the research team during the procedure. This will then be uploaded onto the REDCap database by a delegated member of the research team. Query reports will be run on the database regularly throughout the study and where data is missing or incorrect this will be chased. Missing/incorrect data will also be reviewed and discussed at the Trial Steering Meetings.

### 13.2 Data Management

All data will be handled in line with the Data Protection Act 2018. The data recorded on the paper CRF will be entered onto the REDCap online database by an approved and delegated member of the research team. Where still images are obtained during the colonoscopy these will be uploaded onto the electronic database. Each participating site will have a unique login for the REDCap system. A list of users for the database will be created and will be approved by the Chief Investigator. Information input to REDCap will be anonymised prior to uploading and patients will only be referred to by their participant ID number for all data and images collected. Original paper copies of the CRF will be safely stored according to Good Clinical Practice (GCP)

#### 14. DATA ANALYSIS

## 14.1 Description of Analysis Populations

Analysis will be carried out on an intention to treat basis.

#### 14.2 Analysis of Endpoints

The primary outcome, ADR, will be compared between groups using the Chi-square test. The difference in the proportion of patients with an adenoma detected between groups will be quantified, along with a corresponding 95% confidence interval.

Within both groups, a descriptive analysis of percentage of polyps correctly identified, relative to the histological diagnosis, will be reported.

For all detection outcomes, a series of sensitivity analyses will be performed, repeating the analyses, but this time only considering polyps in the CAD intervention group if they were correctly identified based on their histology.

Binary secondary outcomes will be analysed using the Chi-square test. Continuous secondary outcomes will be compared between groups using the unpaired t-test, if found to be normally distributed, or the Mann-Whitney test otherwise.

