## 10. SAMPLING

- This is powered as a superiority trial.
- For computer aided detection, the ADR of competent but non-expert endoscopists is assumed to be 20% and we believe that CADe will increase it to 30% (expert level). In order to demonstrate a difference of 10% between the two groups with an 80% power and a significance level (alpha) 0.05; we will need 588 patients (294 per group). We will over recruit by 10% (max total of 654) to allow for drop outs, poor bowel prep, incomplete dataset etc. Interim analysis will be done after 50% recruitment
- For computer aided diagnosis, the NPV of endoscopists is assumed to be 75%, and we believe the NPV of endoscopist plus CADx will be 90%. To achieve this with an 80% power and significance level (alpha) of 0.05, we will need to assess 200 diminutive recto-sigmoid (100 per group) polyps (588 total polyps), in an estimated 168 patients. We will plan to over recruit by 10% to allow for incomplete data (220 diminutive recto-sigmoid polyps, 647 total polyps). Interim analysis will be done after 50% recruitment

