### 11.3 Randomisation

Participants will be randomised electronically in a 1:1 ratio into two groups. The intervention group will have their colonoscopy performed with the assistance of the WISE VISION® CAD system, the control arm will have standard colonoscopy. Randomisation will be carried out prior to the procedure being started. The randomisation will be stratified by site to ensure an equal allocation in each centre. Additionally, a blocked randomisation, with varying block sizes, will be performed to allow for a balance between groups throughout the trial.

The randomisation process will be managed using the built-in module within the project's REDCap eCRF database managed by Portsmouth Hospitals University NHS Trust. The Data Manager will generate the randomisation allocation table using statistical software, which will then be uploaded into REDCap before the first patient is consented.

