## 11.4 Study Assessments

Baseline characteristics will be recorded for all participants. Basic demographics will be recorded to include:

- Age
- Sex
- Co-morbidities and ASA score
- History of previous polyps/bowel conditions

During the colonoscopy the following will be recorded in all patients:

- Endoscopist including level of experience (number of life time procedures)
- Indication
- Bowel preparation used and quality
- Use of sedation/general anaesthetic
- Procedure start and finish time and time of maximal intubation
- Comfort score
- Adverse events
- Polyps detected to include the endoscopists optical diagnosis and assessment of size, morphology using the Paris classification, site and details of their removal.
- Still image/video of polyp (where available)

For patients randomised to colonoscopy plus CAD the following additional data will be recorded:

- Total number of potential polyps identified by CADe
- CADx diagnosis of polyps identified
- Outcome of assessment by endoscopist e.g. confirmed as polyp, characterisation assessment

Post colonoscopy:

- Adverse events will be recorded
- Histology of any polyps removed will be recorded to correlate with the endoscopist/CADx assessment of the lesion.

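### The primary ADR test ignores the site stratification used in randomisation; if ADR differs between sites, the test is mildly conservative and its interval slightly too wide

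*Protocol*

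**What the plan says.** Section 11.3 of the protocol sets a 1:1 allocation in blocks of varying size and states: "The randomisation will be stratified by site to ensure an equal allocation in each centre". Section 9.1 lists seven sites: four in the UK, two in Italy and one in Germany.

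Section 14.2 fixes the primary comparison: "The primary outcome, ADR, will be compared between groups using the Chi-square test". The same paragraph adds the between-group difference in the proportion of patients with an adenoma, with a 95% confidence interval. Site appears nowhere in section 14.2.

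Section 10 sizes the detection part on control and intervention ADRs of 20% and 30%: "In order to demonstrate a difference of 10% between the two groups", "with an 80% power and a significance level (alpha) 0.05", giving 294 per group. No section gives site-level ADRs or any measure of between-site variation.

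**The concern.** Blocking within site makes the arms nearly equal in their site mix, so differences in ADR between sites largely cancel out of the treatment comparison. A plain Chi-square and a crude interval do not take account of this. Their standard error is computed as if site mix could differ between arms by chance, so it is too large whenever ADR varies by site.

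Such variation is plausible here. Section 9.3 admits any consenting adult having a colonoscopy, and section 10 itself ties ADR to operator level (20% for non-expert endoscopists, 30% for expert level). At stake is some precision in the headline estimate, which could be had without extra patients. The choice is also not simply left open for a statistical analysis plan, because the protocol names the primary test.

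**Working it through.** **1. The plan's own figure.** Inputs from section 10: p0 = 0.20, p1 = 0.30, power 80%, alpha 0.05 (taken as two-sided; one-sided gives 231 and does not match).

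n = [1.960·√(2·0.25·0.75) + 0.842·√(0.20·0.80 + 0.30·0.70)]² / 0.10² = 293.2, so 294 per group and 588 in total. Power at 294 per group is 80.1%. The stated size reproduces exactly, and it is the size for an unstratified comparison of two proportions.

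**2. What stratification changes.** With equal numbers per arm in each site, the crude and the site-stratified risk differences coincide; only the variance differs. Per arm, the crude variance uses p̄(1−p̄). The within-site variance is p̄(1−p̄) minus the between-site variance of the ADRs. For seven evenly spaced ADRs with step d, that between-site variance is d²(7²−1)/12 = 4d².

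**3. Type I error of the Chi-square (no treatment effect).** Let r be the ratio of within-site to crude variance. The actual level is 2[1 − Φ(1.96/√r)].
- Site ADR 10-35% (assumed): d = 0.25/6, 4d² = 0.00694, p̄(1−p̄) = 0.225·0.775 = 0.1744, r = 0.960. Level = 2[1 − Φ(2.000)] = 4.5%; simulated 4.6%.
- Site ADR 10-50% (assumed): d = 0.40/6, 4d² = 0.01778, p̄(1−p̄) = 0.30·0.70 = 0.21, r = 0.915. Level = 2[1 − Φ(2.049)] = 4.0%; simulated 4.0%.

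**4. Variance under the planned effect.** Apply the odds ratio of 30% against 20%, (0.30/0.70)/(0.20/0.80) = 1.714, at each site.
- 10-35%: the intervention ADRs average 32.7% with between-site variance 0.01137. Crude sum = 0.1744 + 0.2200 = 0.3944. Within-site sum = 0.3944 − 0.0069 − 0.0114 = 0.3761. Ratio 0.954 (simulated 0.957). The half-width of the interval falls from 1.96·√(0.3944/294) = 7.2 points to 1.96·√(0.3761/294) = 7.0 points.
- 10-50%: the intervention ADRs average 41.1% with between-site variance 0.02467. Crude sum = 0.21 + 0.2421 = 0.4521. Within-site sum = 0.4521 − 0.0178 − 0.0247 = 0.4097. Ratio 0.906 (simulated 0.91). The half-width falls from 7.7 to 7.3 points.

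**5. Power, by simulation (7 sites × 42 per arm).**

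| Control ADR across sites (assumed) | Chi-square | Site-stratified CMH | Gain |
|---|---|---|---|
| no variation | 80.0% | 80.0% | 0 |
| 10-35% | 79.7% | 81.0% | 1.3 points |
| 10-50% | 82.1% | 84.5% | 2.4 points |

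These scenarios do not average 20% against 30%. The 79.7% reflects the shifted averages, 22.5% against 32.7%. For these, the two-proportion formula without sites already gives Φ[(0.1018·√294 − 1.96·√(2·0.276·0.724))/√0.3944] = Φ(0.81), about 79%.

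**6. Power with the averages held at 20% and 30%** (40,000 simulated trials per row, site-stratified blocks of 4 and 6, 588 patients in seven equal sites; the spread is the standard deviation of site log-odds).

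| Spread | Control ADR range | Chi-square power | CMH power | Chi-square type I error |
|---|---|---|---|---|
| 0 | 20% | 80.4% | 80.3% | 5.09% |
| 0.25 | 14-27% | 80.3% | 80.5% | 5.05% |
| 0.5 | 9-34% | 80.8% | 81.9% | 4.68% |
| 0.75 | 6-42% | 81.8% | 84.0% | 3.99% |
| 1.0 | 4-49% | 82.3% | 86.1% | 3.64% |

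CMH type I error stayed near 5% throughout. Unequal site sizes gave similar results, with a largest gap of 4.2 points (82.4% against 86.7%).

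**The case against.** The main defence is that a simple prespecified Chi-square is valid here. Its type I error never exceeds the nominal level beyond simulation error, and under 1:1 allocation within site the crude risk difference is a sound marginal estimate. That stands.

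A reader might infer that planned power is lost. The documents do not support this. The 294 per group was computed for the unstratified test, and with average ADRs held at 20% and 30% the Chi-square keeps at least 80% power at every spread examined. What is forgone is a gain over the planned power.

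A reader might also take the conservatism as established. It depends on between-site variation, which the protocol does not give. Mixed indications and the recording of endoscopist experience (section 11.4) make variation plausible, but do not show that sites differ. Gains of 2 points or more need wide spreads.

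It is tempting to extend the point to adenomas per colon, a zero-heavy count that would fall under the generic rule "Continuous secondary outcomes will be compared between groups using the unpaired t-test, if found to be normally distributed, or the Mann-Whitney test otherwise". That rule does not name the endpoint, the Mann-Whitney test is valid for such data, and the model for a secondary count is commonly left to a statistical analysis plan. No calculation here supports the claim that it would merely repeat the ADR test. A supportive model with indication and experience is likewise a preference and forms no part of this point.

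What remains is that the protocol stratifies by site and then names a primary test that ignores it.

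**Conclusion.** The mismatch between sections 11.3 and 14.2 is certain; its cost is conditional and small. If ADR does not vary between sites, nothing is lost. With control ADRs of 10-35%, a site-stratified analysis has about 4% less variance (an interval about 2% narrower) and about 1 more point of power, and the Chi-square runs at about 4.6% instead of 5%. With 10-50%, it has about 9% less variance (an interval about 5% narrower) and about 2.4 more points, and the Chi-square runs at about 4.0%. These figures assume seven equal sites, evenly spaced ADRs and a common odds ratio of 1.714. Neither the validity of the primary test nor the justification of 588 patients is affected. This is an efficiency improvement at no cost in patients.

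**What to change.** In section 14.2, make the primary ADR analysis a Cochran-Mantel-Haenszel test stratified by site, reported with the site-stratified risk difference and its 95% confidence interval. A logistic model adjusted for site, with a standardised risk difference and interval, would serve equally well. Keep the crude Chi-square as a supportive analysis.

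The cost is a change of analysis wording. Site is already known for every patient, no patients or data are added, and the sample size can stay as it is. The change should be settled before any comparison by arm, including the interim analysis planned at 50% recruitment. Section 14.4 sends later deviations to the Trial Steering Committee and, if substantial, to the ethics committee.

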# 2. SYNOPSIS

Study Title	Real time computer aided detection and characterisation of colorectal polyps; a prospective multi-centre randomised controlled superiority trial (ColoVision)
Internal ref. no.	PHU/2022/09
Problem statement	Colorectal cancer is a major health problem. Most colorectal cancers develop from precursor lesions (polyps), and early detection and removal of these polyps can reduce rate and improve outcome of colorectal cancer.
	Colonoscopy is the gold standard test to detect and remove polyps, however there is still significant polyp miss rate. Moreover, the concept of optical diagnosis of polyps has been recommended by various guidelines, however its implementation outside expert and academic centres is still limited.
	Computer aided detection (CADe) and computer aided diagnosis (CADx) of polyps is rapidly progressing and recent studies have shown promising results. However, there is still lack of high-quality data from well-designed and implemented randomised trials and hence the need for this study.
Research question / hypothesis	Our hypothesis is that the CAD device used in this study (WISE VISION®) can significantly improve endoscopists' adenoma detection rate (ADR) as well as their real time optical diagnosis to reach PIVI threshold of 90% NPV, compared to endoscopists not using the CAD device.
Study Design	This is an investigator initiated and led multi-centre randomised control superiority trial. The study will be using the NEC WISE VISION® device which has two functions: CADe and CADx and we will assess the impact of both.
	Participants will be randomised into two groups. The control group will have a standard colonoscopy (without CAD device support), and the intervention group will have colonoscopy with CAD device (both CADe and CADx)
	All patients (both in control and intervention group) will receive standard care. All decisions taken during the colonoscopy procedure will be taken by the endoscopists as per standard protocols.
Study Participants	Patients undergoing a colonoscopy

Planned Sample Size	CADe: 654 participants				
	CADx: 200 diminutive rectosigmoid polyps (588 total polyps)				
Follow-up duration	28 days (+/- 14 days)				
Planned Study Period	12 months				
Primary Objective	
 
To evaluate the impact of the CAD system on endoscopists' detection of colorectal polyps
 
				

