## 8.2 Primary and Secondary Endpoints/Outcome Measures

## **Primary End points**

Adenoma detection rate in both arms PIVI-2: NPV of adenoma diagnosis in diminutive (<5mm) recto-sigmoid polyps in both arms

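### NPV in diminutive rectosigmoid polyps is a powered second primary endpoint, but section 14.2 names only ADR as primary and assigns the NPV comparison no analysis

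*Protocol*

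**What the plan says.** The synopsis (section 2) and section 8.2 each list two primary endpoints. The second is "PIVI-2: NPV of adenoma diagnosis in diminutive (<5mm) recto-sigmoid polyps in both arms". Section 7.1 gives optical diagnosis of diminutive polyps as one of two primary objectives. The synopsis hypothesis is comparative: CAD should improve "real time optical diagnosis to reach PIVI threshold of 90% NPV, compared to endoscopists not using the CAD device".

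Section 10 states "This is powered as a superiority trial" and sizes the two endpoints separately. For optical diagnosis, "the NPV of endoscopists is assumed to be 75" per cent and "we believe the NPV of endoscopist plus CADx will be 90" per cent. With 80% power and alpha 0.05 this gives 200 diminutive rectosigmoid polyps, 100 per group.

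Section 14.2 opens with "The primary outcome, ADR, will be compared between groups using the Chi-square test" and adds a difference in proportions with a 95% confidence interval for ADR. On optical diagnosis it says "Within both groups, a descriptive analysis of percentage of polyps correctly identified, relative to the histological diagnosis, will be reported". The chi-square provision later in that section is confined to binary outcomes that are secondary.

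**The concern.** Section 14.2 does not match the sections that define and size the endpoints. They have two primary endpoints, each with a powered between-arm comparison; section 14.2 has one.

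The one sentence it gives to optical diagnosis differs from the powered endpoint in three ways:

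- It is descriptive and within group, not a comparison of arms.
- Percent correct reads as overall accuracy, which mixes calls of adenoma and non-adenoma. NPV concerns only polyps called non-adenoma.
- It is not limited to diminutive rectosigmoid polyps.

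At stake is whether the second primary question gets a prespecified answer. If the protocol assigns no estimate, interval or test, these can be chosen after the data are seen. The success rule for two primary endpoints is also left open.

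**Working it through.** **1. Was NPV sized for a between-arm test?** Inputs from section 10: p1 = 0.75, p2 = 0.90, power 80%, alpha 0.05. Sidedness is not stated; two-sided is tried first. Allocation is 1:1 (section 11.3).

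n per group = [z(0.975)·√(2·p̄·(1−p̄)) + z(0.80)·√(p1(1−p1) + p2(1−p2))]² / (p2−p1)², with p̄ = 0.825.

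- First term: 1.960 × √0.28875 = 1.053
- Second term: 0.842 × √0.2775 = 0.443
- n = (1.4965)² / 0.0225 = 99.5, so 100 per group

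This is the protocol's figure, and power at 100 per group is 80.2%. The alternatives do not give 100: one-sided 79, unpooled variance 97, continuity-corrected 113. A one-sample comparison of 90% with a fixed 75% gives (1.960·√0.1875 + 0.842·√0.09)² / 0.0225 = 53.9, so 54. The NPV endpoint was therefore sized as a two-sided comparison of arms.

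**2. What does each section assign?**

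| | ADR | NPV, diminutive rectosigmoid |
|---|---|---|
| Primary endpoint (sections 2, 8.2) | yes | yes |
| Powered between arms (section 10) | 20% vs 30%, 294 per group | 75% vs 90%, 100 per group |
| Called primary in 14.2 | yes | no |
| Between-arm test in 14.2 | chi-square | none assigned |
| Estimate with 95% CI in 14.2 | yes | none assigned |

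**3. Can percent correct stand in for NPV?** No. Take an illustration with assumed values: 100 polyps, 60 called non-adenoma with NPV 75% (45 correct) and 40 called adenoma.

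- With positive predictive value 70%: 45 + 28 = 73% correct.
- With positive predictive value 90%: 45 + 36 = 81% correct.

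Percent correct rises by 8 points while NPV stays at 75%.

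**4. Consequences once the test is assigned.**

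- *Success rule.* If either endpoint alone suffices, and the two tests are independent at 0.05 each, the familywise error is 1 − 0.95² = 0.0975. At 0.025 each, 80% power would need 121 polyps and 356 patients per group; NPV power at 100 per group would be 71%. If both endpoints must succeed, no alpha split is needed.
- *Denominator.* NPV is calculated among polyps called non-adenoma, whereas section 10 counts polyps assessed. The protocol gives no proportion called non-adenoma. If 50, 60 or 70 per group are (assumed), power for 75% against 90% is 51%, 58% or 65%.
- *Clustering.* Section 10 expects 200 such polyps in 168 patients, or 1.19 per patient, so some patients must contribute more than one. The formula in step 1 treats polyps as independent.

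**The case against.** **The analysis may be in the statistical analysis plan.** Section 10 already fixes a two-group superiority comparison, and the choice of test could properly sit in a plan not shown here. That holds for the detail of the method. It does not cover section 14.2 calling ADR the primary outcome in the singular. A plan that follows 14.2 would drop the powered NPV comparison; one that follows sections 2, 8.2 and 10 would depart from 14.2. Section 14.4 treats a substantial deviation as a substantial amendment, so the protocol is the place to reconcile this.

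**The descriptive sentence may be an extra, not a replacement.** It names neither NPV nor the polyp subset, and it sits between the ADR analysis and the detection sensitivity analyses. This reading is fair. On it, the NPV comparison is omitted from 14.2 rather than downgraded, and it still has no assigned analysis.

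**A reader might infer that NPV is never tested.** The protocol does not support that. Section 8.2 lists NPV among the secondary diagnostic performance measures, and the chi-square line for binary secondary outcomes could cover it. The primary endpoint also refers to both arms, so per-arm values are foreseen. What remains is that such a comparison would be secondary and not restricted to diminutive rectosigmoid polyps.

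**A reader might also infer that the trial cannot show the 90% threshold**, because the synopsis speaks of "real time optical diagnosis to reach PIVI threshold of 90% NPV" and section 10 assumes a true value of exactly 90%. With 100 negative calls and true NPV 90%, the observed NPV is at least 90% with probability 0.583, and an exact 95% lower limit above 90% (96 of 100 correct) has probability 0.024. But nothing in the protocol requires a lower limit above 90%, and the hypothesis is framed against control. These figures do not measure the missing analysis.

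**Conclusion.** The contradiction holds. Sections 2, 8.2 and 10 make NPV in diminutive rectosigmoid polyps a primary endpoint with a powered between-arm comparison; section 14.2 recognises only ADR and assigns that comparison no estimate, interval or test. One of two primary comparisons is affected in full.

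The conclusion rests on the protocol's wording and on the exact reproduction of 100 per group under a two-sided two-proportion test. It does not depend on the illustrative accuracy figures or on the 90% threshold argument. The error rate of up to 0.0975 applies only if either endpoint alone counts as success and the tests are independent; the protocol does not say which rule applies.

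**What to change.** In section 14.2:

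- Name both primary endpoints.
- For the second, specify the between-arm difference in NPV among diminutive rectosigmoid polyps called non-adenoma, with a 95% confidence interval and a two-sided test that allows for several polyps per patient.
- State whether success needs both endpoints or either one. If either suffices, state how the overall 0.05 is controlled. A fixed sequence is one option, at the cost that the second endpoint is tested only if the first succeeds. The order should be chosen on its merits, since the present wording of 14.2 is itself what needs correcting.
- Keep percent correct as a supporting description, and report the CAD-arm NPV with its 95% confidence interval beside the 90% threshold.

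The cost is protocol wording and one clustered analysis; adding the test does not itself change the planned sample size. The downside is that clustering and the narrower denominator may leave less than the stated 80% power if fewer than 100 polyps per group are called non-adenoma. The expected number of such calls should therefore be stated alongside the 200 polyps.

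### The sensitivity analyses of detection outcomes count only correctly identified polyps in the CAD arm but all polyps in the control arm, so they can only move the comparison against the device

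*Protocol*

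**What the plan says.** Section 14.2 compares ADR between arms with a chi-square test and no filter: "The difference in the proportion of patients with an adenoma detected between groups will be quantified", with a 95% confidence interval. It then describes, in both arms, the percentage of polyps correctly identified relative to histology. The next sentence sets out sensitivity analyses for all detection outcomes, "repeating the analyses, but this time only considering polyps in the CAD intervention group if they were correctly identified based on their histology". ADR is the primary detection outcome; polyp detection rate (PDR) and adenomas per colon are secondary ones (section 8.2). The control arm is not mentioned in the restriction, no reason is given for treating the arms differently, and the result is not labelled as a bound.

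The data for a two-arm rule are planned. Section 8.1 records the endoscopist's diagnosis in both arms, and section 11.4 collects optical diagnosis and histology for all participants. In the CAD arm the CADx output is recorded as well, and section 14.2 does not say which of these diagnoses decides whether a polyp was correctly identified.

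**The concern.** A sensitivity analysis should ask whether the conclusion survives a reasonable change of assumption. This one measures the two arms by different rules. On the natural reading, an adenoma that was found, removed and confirmed by histology stops counting as detected if its optical label was wrong, but only when the patient was randomised to CAD. That makes a detection outcome depend on characterisation, which section 8.1 treats as a separate element of the study.

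The filter also uses a result that arises after randomisation. Under a true null the comparison is therefore not centred on zero, and the direction of the bias is known in advance. What is at stake is interpretation: a real gain in ADR could look fragile, and no difference could look like harm, because of the counting rule alone.

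**Working it through.** **Inputs from section 10.** Control ADR: "the ADR of competent but non-expert endoscopists is assumed to be 20" per cent. CAD ADR: "we believe that CADe will increase it to 30% (expert level"). Size: "we will need 588 patients (294 per group"), "with an 80% power and a significance level (alpha) 0.05".

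**Input not in the protocol.** The share *s* of CAD-arm adenoma-positive patients who stay positive after the filter. The nearest figure, the 90% NPV in section 10, is not a sensitivity, so a range is shown.

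**Step 1: reproduce the plan's figure.** Two-sided test, pooled variance, no continuity correction:

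n = [1.960 × √(2 × 0.25 × 0.75) + 0.842 × √(0.20 × 0.80 + 0.30 × 0.70)]² / 0.10² = (1.200 + 0.512)² / 0.01 ≈ 293.2, so 294 per arm and 588 in total. Then 588 / 0.90 = 653.3, so 654. Both match. Power at 294 per arm is 80.1%.

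**Step 2: one-arm filter, one adenoma per positive patient.** CAD ADR becomes 0.30 × *s* and control stays at 0.20. If there is no true effect, the difference is 0.20 × *s* − 0.20. For comparison, the same filter in both arms with equal *s* gives (0.30 − 0.20) × *s*, and zero under the null.

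| *s* | CAD ADR | Difference, CAD-only filter | Power | Difference if no true effect | Difference, both arms filtered | Power |
|---|---|---|---|---|---|---|
| 0.95 | 28.5% | 8.5 points | 67% | -1.0 | 9.5 points | 77% |
| 0.90 | 27.0% | 7.0 points | 52% | -2.0 | 9.0 points | 74% |
| 0.85 | 25.5% | 5.5 points | 36% | -3.0 | 8.5 points | 71% |
| 0.80 | 24.0% | 4.0 points | 22% | -4.0 | 8.0 points | 68% |

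The difference would be halved when 0.30 × *s* − 0.20 = 0.05, that is *s* = 0.833, or one in six CAD-arm positive patients lost.

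**Step 3: several adenomas per positive patient.** A patient stays ADR-positive if any one adenoma is correctly labelled. Assume a zero-truncated Poisson number of adenomas among positive patients and independent labels with per-adenoma correctness *c*. Then *s* = (1 − e^(−λc)) / (1 − e^(−λ)). A mean of two requires λ / (1 − e^(−λ)) = 2, so λ ≈ 1.59.

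| *c* | Difference, mean 1.5 adenomas | Difference, mean 2 adenomas |
|---|---|---|
| 0.90 | 8.0 points | 8.7 points |
| 0.85 | 7.0 points | 7.9 points |
| 0.80 | 5.9 points | 7.1 points |

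Halving now needs *c* of about 0.76 (mean 1.5) or 0.68 (mean 2). This protection applies to ADR only. For adenomas per colon every mislabelled adenoma is lost, so the CAD-arm mean is multiplied by *c* whatever the number per patient.

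**Step 4: the other reading of the filter.** If correctly identified means only that histology confirmed a real lesion, ADR hardly moves, because adenoma status itself rests on histology. PDR does move: the CAD arm would count histologically confirmed polyps and the control arm every polyp recorded.

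**The case against.** The strongest objection is about meaning. The sentence concerns detection, the protocol has an objective on CADe false positives (section 7.2), and section 11.4 records, for the CAD arm only, how many potential polyps CADe flagged and whether the endoscopist confirmed them. The filter may have been meant to stop false alarms inflating PDR. That reading is possible and should be disclosed. The sentence just before it in section 14.2 uses correct identification in the sense of agreement with the histological diagnosis, which makes diagnostic correctness the likelier meaning. Even on the other reading, PDR would be counted by different rules in the two arms.

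Second, the size is assumed. No per-adenoma sensitivity is given, and one adenoma per positive patient is the most damaging case. Section 10 expects 588 polyps in an estimated 168 patients, which is 588 / 168 = 3.5 per patient. These are not all adenomas, but the figure sits poorly with a single lesion each. This stands. A reader might infer that the analysis halves the ADR effect by construction; the protocol does not support that. Only the direction is built in.

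Third, a bound of known direction can be legitimate, since a gain that survives it is strengthened. That is true of a labelled bound, but the protocol neither states that intent nor labels the result.

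**Conclusion.** The point holds as a fault in a sensitivity analysis. The direction is certain: as written, the filter can reduce CAD-arm detection and cannot increase it, so a true null would tend to appear as harm. The size is conditional. At the planned rates the 10-point difference shrinks to between 4.0 and 7.0 points with 80% to 90% of positive patients kept and one adenoma each, or to between about 7.1 and 8.7 points with a mean of two adenomas and the same per-adenoma correctness. Most of the loss in the one-adenoma case comes from the asymmetry, since an equal filter in both arms keeps 8.0 to 9.0 points.

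A reader might also infer that the trial's main conclusion is compromised. It is not: the primary ADR test is unfiltered, its sample size reproduces exactly, and nothing in the protocol ties the conclusion to this sensitivity analysis. The power figures above only show how weak the filtered comparison would be; the trial was not sized for it.

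**What to change.** Change the one sentence in section 14.2, in one of two ways.

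- Apply the same rule in both arms, using the optical diagnosis and histology already recorded. State whose diagnosis counts (endoscopist, CADx or combined). Report the result as a secondary composite, 'detected and correctly characterised', and not as a robustness check on detection.
- Or delete the one-arm analysis for detection outcomes.

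If the aim was to guard against CADe false positives, count only histologically confirmed polyps in both arms.

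No new data are needed. The symmetric composite has a price: it mixes detection with characterisation and could favour the CAD arm if CADx improves characterisation. For illustration, with no difference in detection (20% in both arms) and assumed shares kept of 0.90 with CAD and 0.80 without, it would show 0.20 × (0.90 − 0.80) = +2 points. It must therefore be labelled as a composite.
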